- participant on a NOAC in case of at least one bleeding risk feature (history of a prior bleed within the last 12 months requiring medical attention and / or moderate renal dysfunction with eGFR 30-50 ml/min and / or current clinically indicated antiplatelet therapy with acetylsalicylic acid [ASA] ≤ 100 mg).

Stratification will be based on whether participants received a NOAC before study start or were not treated with any oral anticoagulant.

The planned study duration will be 14-16 weeks, consisting of:

- Screening period (visit 1 until visit 2): 2 weeks (participants will be screened and have to be randomized within 2 weeks of screening. If all information is available, a participant can be randomized on the day of screening (visits 1 and 2 are combined).
- Treatment period (from visit 2 through visit 6 [EOT] or visit 6a [ET]): 12 weeks
- Safety follow-up (visit 7 [SFU]): 14 days (+ 7 days) after EOT or ET.

Study visits will take place as visits at the study sites and telephone calls. Visits at the study sites take place at screening and randomization (visit 1 and visit 2), at week 4 (visit 4) and week 12 (i.e. EOT, visit 6).

[figure not shown]
Telephone calls will take place at week 2 (visit 3), week 8 (visit 5), as well as 2 weeks after the EOT visit for participants who will take study intervention until the planned EOT (i.e. SFU, visit 7).

For participants who prematurely discontinue from study intervention, an early termination (ET) visit (visit 6a) will take place as soon as possible as visit at the study sites. Telephone calls take place 14 days after the ET visit (i.e. SFU, visit 7).

The study design is presented in Figure 3-1: Study design overview.

Page: 7 of 25:

Figure 3-1: Study design overview

Duration of Treatment: 12 weeks

Note: Participants receiving BAY 2433334 will also receive the apixaban matching placebo. Participants receiving apixaban will also receive the BAY 2433334 matching placebo. During the safety follow-up, further therapy (e.g. NOAC) is at discretion of the investigator.

4. General Statistical Considerations

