4.5.2 Data Scopes

Treatment emergent data scope

For the treatment emergent data scope all events from first intake of study drug up until 2 days after the last intake of study treatment will be counted. The time to event for participants with no event until 2 days after the last intake of study drug (end of data scope) will be censored at that day.

For events at the day of randomization will be counted if the time of occurrence is later than the time of first study drug intake.

This data scope will be used to handle intercurrent events according to the "while on treatment" strategy.

Intention-to-treat (ITT) data scope

For the intention-to-treat (ITT) data scope all events from randomization up until end of treatment visit (Visit 6) (end of data scope) will be counted. The time to event for participants with no event up until the end of treatment visit will be censored at that day.

This data scope will be used to handle intercurrent events according to the "treatment policy" strategy.

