4.5.3 Time-to-Event variables

For the treatment emergent data scope, the time from first intake of study drug to an event is of interest. The time to an event (in days) will be derived the following:

Date of Event – Date of first study drug intake + 1.

For time to event variables in the intention-to-treat (ITT) data scope the time from randomization to an event is of interest. The time to an event (in days) will be derived the following:

Date of Event – Date of randomization + 1.

Survival functions, incidence rates and cumulative hazard calculations will be done only for endpoints with at least 3 events in at least one treatment arm. (Cause specific) hazard ratios (csHR) will be calculated only if in addition at least 1 event in each of the compared treatment arm occur.

If treatment arms are pooled the number of events needed applies on the pooled arm not on each treatment arm.

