6.2 Efficacy

Efficacy analyses in this study will be exploratory only.

Exploratory endpoints for this study are:

- the composite as well as individual components of CV death, MI, ischemic stroke, • and systemic embolism,
- all-cause mortality. •

Events will be counted in the intention-to-treat data scope for the full analysis set.

The number of participants with an efficacy endpoint and percentages will be shown by treatment arm.

Taking the time under risk into account, the exposure-adjusted incidence rate will be calculated for each treatment arm with an 90% confidence interval.

The incidence rate (IR) will be expressed as "participants with an event per 100 participant years". For that the following formula (Unkel, et al. 2019) is used:

$$IR = \frac{\# Participants with an event}{\sum time \ to \ event \ (or \ censoring)(in \ days)/(100 * 365.25)}$$

The 90% confidence interval for the IR will be computed as

$$\left[\frac{IR * \chi^2(0.05; 2e)}{2e}; \frac{IR * \chi^2(0.95; 2e)}{2e}\right],$$

with $\chi^2(q; 2e)$ the q quantile of a chi square distribution with 2e degrees of freedoms and e the number of participants with an event. (Nelson 1982)

In addition, time-to-first-event analyses taking competing events into account will be performed. For that Aalen-Johansen estimates for the cause specific cumulative risk will be presented.

The competing event for the efficacy events is death or non-CV death for endpoints that include CV death. There will be no competing event for all-cause mortality.

The cumulative incidence, i.e. the probability of having a specific event E at or before a timepoint t, $P(T \le t, E = 1)$, will be estimated for time-to-event endpoints by Aalen-Johansen estimators with the competing event as defined before. For the Aalen-Johansen estimator the cumulative hazard calculated by the cause-specific Nelson-Aalen estimator is needed. The calculation of the estimators follows Allignol, Beyersmann and Schmoor (Allignol, Beyersmann and Schmoor 2016).

The cause-specific Nelson-Aalen estimator for an event E at timepoint t is calculated as:

$$\hat{\Lambda}_E(t) = \sum_{t_j \le t} \frac{\#Participants \text{ with an event } E \text{ at } t_j}{\#Participants \text{ under risk at } t_j}.$$

The Aalen-Johansen estimator takes the difference of the cause-specific Nelson-Aalen estimator into account, weighted with the Kaplan-Meier (KM) survival function, i.e. the Aalen-Johansen estimator for time t is defined as:

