6.4.1.2 Primary Safety Analyses

The primary estimator is the ratio of incidence proportions of the primary safety endpoint observed in participants who are under treatment with BAY 2433334 (all doses pooled) and the active comparator for up to 12 weeks with corresponding 90% confidence interval.

The (crude) incidence proportion of the primary safety endpoint is defined as the number participants with an event in 12 weeks while the participant is under exposure of study drug (counting treatment according to the treatment emergent data scope) divided by the number of participants in the treatment arm who took at least one dose of study drug, (the SAF population) i.e.

 $\widehat{CI}_{A} = \frac{\#Participants \text{ with an event}}{\#Participants \text{ that took at least one dose of study drug }A}.$

These incidences proportions will be estimated for BAY 2433334 arm (all doses pooled) and the apixaban arm. The main estimator for this study is the ratio of the (crude) incidence proportions

$$\widehat{CIR} = \frac{\widehat{CI}_{BAY \ 2433334}}{\widehat{CI}_{Apixaban}}$$

The corresponding 90% two-sided confidence interval will be calculated using the Farrington-Manning score for an exact confidence interval. The calculation of the ratio of crude incidences and the confidence intervals will be done by using SAS code corresponding to the following:

Taking the time under risk into account, the exposure-adjusted incidence rate will be calculated for each treatment arm with an 90% confidence interval.

The exposure-adjusted incidence rate will be expressed a "subjects with an event – per 100 participant years". For that the following formula is used:

 $IR_{adj} = \frac{\#Participants with an event}{\sum time under treatment (in days)/(100 * 365.25)}$

The 90% confidence interval for the exposure-adjusted IR will be computed as

$$\left[\frac{IR_{adj} * \chi^2(0.05; 2e)}{2e}; \frac{IR_{adj} * \chi^2(0.95; 2e)}{2e}\right]$$

with $\chi^2(q; 2e)$ the q quantile of a chi square distribution with 2e degrees of freedoms and e the number of participants with an event. (Nelson 1982)

In addition to the main analysis, time-to-first-event analyses taking competing events into account will be performed. For that Aalen-Johansen estimates for the cause specific cumulative risk will be presented.

The competing events for the primary safety endpoint are Death (all causes) and premature discontinuation.

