The cumulative incidence risk, i.e. the probability of having a specific event E at or before a timepoint t, $P(T \le t, E = 1)$, will be estimated for time-to-event endpoints by Aalen-Johansen estimators with the competing event as defined in section 6.2.

The difference of the Aalen-Johansen estimators at day 85 (week 12) between BAY 2433334 treatment and Apixaban will be presented with a 90% confidence interval.

As the Aalen-Johansen estimator is approximately normal distributed (Aalen, Borgan and Gjessing 2008), the difference of Aalen-Johansen estimators is approximately normal distributed. Thus, the two-sided 90% confidence interval is obtained via:

Page: 21 of 25:

$$\left[(\widehat{A}J^{BAY}(85) - \widehat{A}J^{Apixaban}(85)) \pm z_{0.95} \sqrt{\sigma^2(\widehat{A}J^{BAY}(85)) + \sigma^2(\widehat{A}J^{BAY}(85))} \right]$$

with $\widehat{AJ}^{TRT}(85)$ the Aalen-Johansen estimator for treatment TRT at day 85, $z_{0.95}$ the 95% quantile of the standard normal distribution and $\sigma^2(\widehat{AJ}^{TRT}(85))$ the estimated variance of the Aalen-Johansen estimator at day 85, estimated with the Aalen method.

All analyses will be done for the pooled doses of BAY 2433334 and for each of the two doses.

csHRs will be calculated for the respective event and the competing event. Gray's test of equivalence of the cumulative incidence functions, stratified by prior usage of NOAC, will be performed. The cause specific hazard ratios and the corresponding confidence intervals will be estimated on separate models for the pooled doses of BAY 2433334 and each comparison (if applicable). No comparison of the different doses of BAY 2433334 is planned.

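### The 90% interval for incidence rates (SAP 6.2 and 6.4.1.2) uses 2e degrees of freedom at both ends, so its upper limit is the exact Poisson limit for one event fewer than observed, and it is undefined at zero events

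*SAP*

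**What the plan says.** Sections 6.2 (efficacy) and 6.4.1.2 (primary safety) give the same 90% interval for a rate per 100 participant-years. The lower limit is IR × χ²(0.05; 2e)/(2e) and the upper limit is IR × χ²(0.95; 2e)/(2e). Section 6.4.1.2 defines the quantile as "the q quantile of a chi square distribution with 2e degrees of freedoms and e the number of participants with an event", so the formula and the text agree on 2e at both ends.

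Observation ends by time:

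- Section 3: "Treatment period (from visit 2 through visit 6 [EOT] or visit 6a [ET]): 12 weeks".
- Section 4.5.2, treatment-emergent scope: events "from first intake of study drug up until 2 days after the last intake of study treatment will be counted".
- Section 4.5.2, intention-to-treat scope: "The time to event for participants with no event up until the end of treatment visit will be censored at that day".

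Section 4.5.3 sets the display rule: "incidence rates and cumulative hazard calculations will be done only for endpoints with at least 3 events in at least one treatment arm". Sections 6.4.1.3 (secondary bleeding endpoints) and 6.4.2 (subgroups) are stricter and show rates only in arms that themselves have 3 or more events. For the primary safety endpoint, 6.4.1.2 adds: "All analyses will be done for the pooled doses of BAY 2433334 and for each of the two doses".

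**The concern.** A chi-square interval with 2e at both ends is exact when e is fixed in advance and the time needed to reach it is random. This trial does the reverse: time is limited and e is random. For a Poisson count over fixed time, the lower limit uses 2e and the upper limit uses 2e+2. The plan's lower limit is therefore right and its upper limit too low.

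For a bleeding or cardiovascular event rate, the upper limit tells the reader how high the rate could plausibly be. The shortfall is largest at low counts. Low counts are plausible, because the Introduction expects a low bleeding risk and the primary safety analyses are repeated for each single dose.

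There is also a gap at zero events. Under 4.5.3 a primary-safety or efficacy rate can be shown for an arm with 0, 1 or 2 events once another arm has 3. At e = 0 the rate is 0, but the interval is 0/0.

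**Working it through.** The SAP prints no numerical limit, so there is no figure of its own to reproduce. The inputs are the 90% level (5% per tail) and the 2e degrees of freedom (6.2, 6.4.1.2), time-ended follow-up (3, 4.5.2) and the 3-event display rules (4.5.3, 6.4.1.3, 6.4.2). On the scale of expected events, person-time cancels from every ratio below.

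**Which count does the upper limit belong to?** Take e = 3 and X Poisson.

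- Written upper limit: χ²(0.95; 6)/2 = 6.296. At that mean P(X ≤ 2) = 0.050 and P(X ≤ 3) = 0.127. It is the exact 95% upper limit for 2 events. For the 3 events observed, the tail is 12.7% instead of 5%.
- Written lower limit: χ²(0.05; 6)/2 = 0.818. At that mean P(X ≥ 3) = 0.050, as it should be.
- Fixed-time upper limit: χ²(0.95; 8)/2 = 7.754. At that mean P(X ≤ 3) = 0.050.
- Shortfall: 1 − 6.296/7.754 = 18.8%. Against 2e+1 it is 1 − 6.296/7.034 = 10.5%.

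**Upper limit in expected events**

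| e | 2e (SAP) | 2e+1 | 2e+2 | SAP below 2e+1 | SAP below 2e+2 |
|---|---|---|---|---|---|
| 1 | 3.00 | 3.91 | 4.74 | 23.3% | 36.9% |
| 2 | 4.74 | 5.54 | 6.30 | 14.3% | 24.7% |
| 3 | 6.30 | 7.03 | 7.75 | 10.5% | 18.8% |
| 5 | 9.15 | 9.84 | 10.51 | 7.0% | 12.9% |
| 10 | 15.7 | 16.3 | 17.0 | 3.9% | 7.4% |
| 20 | 27.9 | 28.5 | 29.1 | 2.1% | 4.1% |

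**Exact Poisson performance, averaged over 3 to 30 expected events.** The range is an assumption, because the SAP gives no arm size or event rate. As written, e = 0 counts as a miss.

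| | 2e (SAP) | 2e+1 | 2e+2 |
|---|---|---|---|
| Upper-side miss (nominal 5%) | 7.2% | 5.1% | 3.6% |
| Lower-side miss (nominal 5%) | 3.9% | 3.9% | 3.9% |
| Two-sided coverage (nominal 90%) | 88.8% | 91.0% | 92.5% |
| Share of expected counts with coverage below 90% | 72% | 21% | none |

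As written, the upper-side miss runs from 5.0% to 19.9%. With 2e+2 it never exceeds 5.0%. Coverage as written is 76.7% at 3 expected events and 84.4% at 5. By range, coverage as written against 2e+2 is 88.0% vs 93.1% over 3 to 15 and 89.4% vs 92.2% over 10 to 30.

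**Only arms with 3 or more events** (secondary endpoints and subgroups). Over 3 to 15 expected events the upper-side miss is 5.0% as written and 2.0% with 2e+2, and coverage is 91.1% and 94.1%. The lowest coverage as written is 85.1%, near 9.2 expected events. Over 10 to 30 the restriction hardly matters: upper-side miss 6.6% vs 3.8%, coverage 89.4% vs 92.2%.

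**Does the Poisson model mislead?** Only first events count and person-time is random, so neither formula is exact here. A simulation with assumed values (250 participants per arm, at most 86 days, 10% dropout, 20,000 runs) gave coverage as written against 2e+2 of 84.7% vs 93.2% at 5 expected events, 88.4% vs 92.4% at 12 and 89.9% vs 92.4% at 20. The pattern is the same.

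**The case against.** The strongest reply is that no printed number is wrong. The plan chose one approximate interval, with a textbook citation, over a more conservative one. On average two-sided coverage its choice is nearer to 90%: the mean distance from 90% over 3 to 30 expected events is 1.5 points as written, 2.5 with 2e+2 and 1.3 with 2e+1. In tables limited to arms with 3 or more events, the change makes average calibration worse. The 76.7% also counts zero-event arms, for which no interval can be printed; among arms with at least one event the minimum is 80.8%.

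These figures are correct and they limit the weight of the point. They do not remove it. The better average arises because a lower-side miss below 5% offsets an upper-side miss that, counting all outcomes, is never below 5%. For an adverse-event rate the two sides are not interchangeable. The 3-event restriction does not govern the primary-safety and efficacy rates. The cited textbook was not available to check, but a citation cannot change how follow-up ends in this trial. The zero-event gap does not depend on any view about coverage.

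**Conclusion.** The concern holds and is minor. With follow-up ended by time, the written upper limit belongs to e−1 events and is always too low against the standard fixed-time limit: by 18.8% at 3 events, 7.4% at 10 and 4.1% at 20. Because 2e+2 is itself conservative, these are the upper end of the shortfall; against 2e+1 it is 10.5%, 3.9% and 2.1%. The practical effect is mainly in primary-safety and efficacy arms with few events. Secondary and subgroup tables with few expected events are on target on average as written.

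The primary and secondary ratios of proportions, the Aalen-Johansen difference, Gray's test and the hazard ratios do not use this formula, and efficacy is exploratory, so no main result changes. The limits and shortfalls rest only on the formula and the time-ended design. The coverage figures also rest on the Poisson model and the assumed ranges of expected events.

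**What to change.** In 6.2 and 6.4.1.2, change the upper limit to IR × χ²(0.95; 2e+2)/(2e) and keep the lower limit. Add one sentence for e = 0 in the primary-safety and efficacy rates: lower limit 0, and upper limit χ²(0.95; 2)/2 = 3.00 events divided by person-time in units of 100 participant-years.

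The cost is one term in two formulas and one sentence. The intervals become slightly conservative, with average coverage of about 92–93% instead of 88–89% and an average upper-side miss of 3–4%. In arms shown only with 3 or more events and few expected events they become clearly conservative (94.1% over 3 to 15). If the sponsor prefers average coverage close to 90%, 2e+1 is a defensible compromise, but it gives up the guarantee that the upper-side miss stays at or below 5%. Under either choice the zero-event sentence is needed.

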4.5.4 Special cases of censoring

In special cases, the censoring differs from the section before.

If no event is observed, the censoring date will be determined by the following:

- In case of death of the participant before visit 6:
 - the date of the death.
- In case the participant dies after the end of treatment visit (visit 6) but before the safety follow-up (visit 7)
 - the censoring date according to the "treatment policy" strategy is the date of visit 6
 - the censoring date according to the "while on treatment" strategy is the earliest of 2 days after last study drug intake and the date of death.
- In case the participant is lost to follow up before end of data scope
 - the last study contact date, defined as the latest date of any visit date and dates of any (outcome) events
 - if the vital status is known alive at any date after the last study contact date: for the event death (including CV and non-CV-death): the date of this information.
- In case the participant withdraws consent before end of data scope
 - the date of withdrawal of informed consent

• if the vital status is known alive at any date after the last study contact date: for the event death (including CV and non CV-death): the date of this information.

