6.1.1 Disposition

The following will be tabulated by treatment group and overall:

- Study sample sizes by region and country
- Study sample sizes by country and site
- Participants disposition
- Number of participants and primary reasons for screening failures
- Number of participants and primary reasons for premature discontinuation of study medication
- Number of participants and primary reasons for premature discontinuation of study follow up.

Incidences for permanent discontinuation of the double-blinded study drug and of the followup period will be provided by randomized study treatment groups, based on the case report form data.

Kaplan-Meier estimates will be used to present

- time to the date of last double-blind dose of study treatment,
- time to the date of last follow-up contact,

all calculated as days from randomization, by study treatment group.

Other details regarding visit adherence (e.g., visit completed in person, by telephone, through third party) and completion as well as study drug adherence collected via CRFs will be summarized using frequency tables by visit and study treatment group.

6.1.2 **Protocol Deviations**

No per protocol analysis set will be defined in this study. The number of participants with major protocol deviations and validity findings according to the CRF will be summarized by study treatment group as well as reasons.

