6.4.3 Analyses related to COVID-19

Analysis due to COVID-19 pandemic will be described in this section but might affect all sections of the analyses.

A description of the number of study participants whose assessments and follow up in the study was impacted by the COVID-19 pandemic will be shown. In addition, a listing of all study participants affected by the COVID-19 pandemic by unique subject number identifier and by investigational site, and a description of how the individual's participation was altered will be created.

For the primary safety estimand the intercurrent event "Treatment discontinuation due to COVID-19 related events" will be handled similar to any other premature discontinuation, i.e. all events from first intake of study drug up until 2 days after the last intake of study treatment will be counted.

Subgroup analyses for incidence tables will include the subgroup "Participants that are effected to any site closing due to COVID-19" will include all subjects that are randomized at sites that are closed due to COVID-19 before their individual end of treatment visit, resp. last study contact date, whatever is earlier. If there are more than one phase of closing in a site no distinction between the phases will be done.

Page: 23 of 25:

Demographics, Medical history as well of the tables showing the number of participants with an efficacy or safety event will be additionally shown for this subgroup.

Protocotol deviations due to COVID-19 will be shown in the protocol deviations section as a separate category.

COVID-19 disease itself will be counted as an adverse event and therefore listed in the repective adverse event tables

If the number of patients with a dignosed COVID-19 disease is sufficiently high (i.e. 10 participants or more), the following sensitivity analyses will be done for the efficacy and safety outcomes:

The primary estimand will handle the COVID-19 disease with an "while not having COVID-19 disease" approach and censor any patients data 14 days before the (first) start of a COVID-19 disease.

In addition the number of subjects with an event occurring after COVID-19 disease will be shown for efficacy and safety events.

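### SAP 6.4.1.2 takes the competing event for the bleeding Aalen-Johansen estimator from section 6.2, which covers only efficacy events and omits the premature discontinuation that 6.4.1.2 itself has just named

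*SAP*

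**What the plan says.** Section 6.4.1.2 makes the ratio of crude incidence proportions the main analysis and adds time-to-first-event analyses with competing events. It states: "The competing events for the primary safety endpoint are Death (all causes) and premature discontinuation". The next paragraph, which defines the cumulative incidence to be estimated, says it is obtained "by Aalen-Johansen estimators with the competing event as defined in section 6.2".

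Section 6.2 says: "The competing event for the efficacy events is death or non-CV death for endpoints that include CV death". It does not mention discontinuation. Its analyses use the full analysis set and the intention-to-treat scope, in which stopping drug does not end follow-up. The bleeding analyses use the treatment-emergent scope of section 4.5.2, under which "participants with no event until 2 days after the last intake of study drug (end of data scope) will be censored at that day".

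The code comment in section 6.2 separates status 0 (right-censored), 1 (event of interest) and 2 (competing event). Section 6.4.1.3 extends Aalen-Johansen estimates to the four secondary bleeding endpoints, in arms with 3 or more events. Section 6.4.1.4 has the seven exploratory bleeding endpoints follow the same estimation. Neither section names a competing event of its own.

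**The concern.** The two adjacent statements in 6.4.1.2 give different status codes to every participant who stops study drug without a bleed: 2 under the first, 0 under the second. The second is the sentence that defines the estimator, so a programmer who follows its reference arrives at a rule without discontinuation.

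The codes answer different questions. With discontinuation as a competing event, the curve is the probability of a bleed while the participant is alive and on drug, which is the estimand in 6.4.1.1. With discontinuers censored, it is the bleeding risk that would be seen if nobody stopped the drug, assuming that stopping is unrelated to bleeding risk. The affected outputs are the Aalen-Johansen curves, the day-85 difference with its 90% interval, Gray's test, and the cause-specific hazard ratio for the competing event, which would then rest on deaths alone.

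**Working it through.** **Side-by-side reading**

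| Place in the SAP | Applies to | Competing event | Event-free discontinuer |
|---|---|---|---|
| 6.4.1.2, statement for the primary safety endpoint | bleeding | all-cause death, premature discontinuation | status 2 |
| 6.4.1.2, estimator sentence, through 6.2 | efficacy events by 6.2's own terms | death, or non-CV death | status 0 |

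The SAP states no figure on this point, so there is none to reproduce.

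**Illustration of size**

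All rates are assumed: constant, independent hazards over 85 days, deaths ignored, order BAY 2433334 v apixaban. Let b be the day-85 bleeding risk under censoring and d the day-85 discontinuation probability.

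- Hazards: λb = −ln(1−b)/85 and λd = −ln(1−d)/85.
- Censoring: risk = b.
- Competing event: risk = λb/(λb+λd) × [1 − exp(−85(λb+λd))].

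Example, b = 5% and d = 10%: λb = 0.000603 and λd = 0.001240 per day. The last factor is 1 − 0.95×0.90 = 0.145, and the risk is 0.000603/0.001843 × 0.145 = 4.75%.

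One arm, b = 5%:

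| d | Censored | Competing | Relative excess of censored |
|---|---|---|---|
| 5% | 5.00% | 4.88% | 2.6% |
| 10% | 5.00% | 4.75% | 5.3% |
| 15% | 5.00% | 4.62% | 8.3% |
| 20% | 5.00% | 4.49% | 11.5% |

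Day-85 difference in percentage points:

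| Bleeding | Censored | Competing, d = 8% v 15% | d = 10% v 10% | d = 15% v 8% |
|---|---|---|---|---|
| 2.5% v 5% | −2.50 | 2.399 − 4.618 = −2.22 | −2.37 | −2.49 |
| 7% v 10% | −3.00 | 6.719 − 9.243 = −2.52 | −2.85 | −3.13 |
| 5% v 5% | 0.00 | 4.799 − 4.618 = +0.18 | 0.00 | −0.18 |

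The largest shifts are 0.28 points in the first row and 0.48 in the second. To scale them, take an assumed 500 v 250 participants and a 90% interval:

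- 2.5% v 5%: half-width = 1.645 × √(0.025×0.975/500 + 0.05×0.95/250) = 2.54 points, and 0.28/2.54 = 11%.
- 7% v 10%: half-width = 1.645 × √(0.07×0.93/500 + 0.10×0.90/250) = 3.64 points, and 0.48/3.64 = 13%.

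Competing-event hazard ratio at 8% v 15% discontinuation: ln(0.92)/ln(0.85) = 0.51, or 0.54 with 1% deaths added to each arm. This only restates the assumed discontinuation rates. It shows what the output describes under one code and omits under the other.

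**What does not change**

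The crude ratio uses no competing-event status. The bleeding hazard ratio removes a discontinuer from the risk set under either code, so it is the same when the date is the same.

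**The case against.** The strongest reply is that this is a slip of reference and the intention is clear. The specific statement for the primary safety endpoint comes directly before the faulty sentence, and section 6.2 limits its rule to efficacy events. The Aalen-Johansen formulas stand in 6.2, so a pointer there has an obvious use, and the sentence looks carried over from that section. This is probably right about the intention. It does not cure the text: the pointer is attached to the competing event, not to the formulas, and nothing says which statement prevails.

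A reader might infer more than the SAP supports in four respects.

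- *That 4.5.2 separately contradicts 6.4.1.2 by censoring discontinuers.* Section 4.5.4 also gives the date of death as a censoring date, although death is a competing event. Section 4.5.2 is therefore better read as fixing a date than a status.
- *That it is open what is discontinued.* Section 6.1.1 does use the term for both, with "Number of participants and primary reasons for premature discontinuation of study medication" and "Number of participants and primary reasons for premature discontinuation of study follow up", but it is a list of tables and spells out each type. The estimand, the while-on-treatment scope and section 6.4.3 ("handled similar to any other premature discontinuation, i.e. all events from first intake of study drug up until 2 days after the last intake") all point to study drug. Confirmation is enough.
- *That every output carries over to the other bleeding endpoints.* For the secondary endpoints, 6.4.1.3 adds only exposure-adjusted rates and Aalen-Johansen estimates to the crude ratio. It does not expressly call for the day-85 difference, Gray's test or hazard ratios.
- *That the status of participants lost to follow-up or withdrawing consent is also wrong.* Section 4.5.4 gives them dates of their own ("In case the participant is lost to follow up before end of data scope"). Prescribing a status for them would be a new choice, not a correction.

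**Conclusion.** The reference to section 6.2 is wrong as written and should be corrected. Severity is minor. The error touches supportive analyses only, and the adjacent sentence shows the likely intention. Followed literally, it changes what the Aalen-Johansen analyses estimate.

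The sizes rest entirely on assumed bleeding rates, discontinuation rates and arm sizes, and on constant independent hazards. Within those ranges the shift in the day-85 difference stays at or below about 0.5 points and is small beside the interval width. It is largest when discontinuation differs between arms. No figure is offered for Gray's test, because the SAP's test is stratified and gives no rates to work from. The documents do not support a claim that the primary conclusion is at risk.

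**What to change.** - In 6.4.1.2, replace the pointer to section 6.2 in the estimator sentence with the competing events already named there: all-cause death and premature discontinuation of study drug. The sponsor should confirm the study-drug reading.
- State that the same definition applies to the Aalen-Johansen estimates of the secondary and exploratory bleeding endpoints.
- State that an event-free discontinuer is coded as a competing event (status 2), dated at the end of the 2-day window after last intake. The date matters: if the competing event fell on the day of stopping, bleeds in the following 2 days, which 4.5.2 counts, would drop out of these analyses.
- Leave section 6.2's definition as it is for efficacy.

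The cost is a few lines of SAP wording and one status derivation in the bleeding time-to-event dataset. No new data are needed.
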